In the recent years, the aim of IBD treatment has evolved from symptomatic control to deep remission, which is defined as the absence of symptoms, markers of inflammatory activity, and endoscopic lesions, and is associated with fewer admissions to hospital, surgeries and better HRQoL. Main current treatment modalities for UC and CD include 5-aminosalicylates, corticosteroids, immunomodulators (including thiopurines, methotrexate, tacrolimus, cyclosporine, and biological therapies), and surgery. Conventional treatment with corticosteroids and immunomodulators has not been able to reduce the complications of the disease or modify its course. Over the last decade, biologic treatments, such as infliximab, adalimumab, certolizumab pegol, golimumab and vedolizumab has been used in patients with moderate to severe CD, and in those with acute severe UC who failed to respond to corticosteroids.

At present, early introduction of immunomodulators and biologic agents in patients with more serious disease is probably the most widely accepted management strategy. Treatment of IBD with anti-TNF $\alpha$  since IBD diagnosis, albeit capable of inducing and maintaining mucosal healing and reducing surgery and hospitalization rates, may imply overtreatment of patients with milder forms of disease, thus emphasizing the need for accurate prognostic markers to guide patient selection. It is worth mentioning that although anti-TNF $\alpha$  therapy is thought to be an effective approach for IBD, up to 30% of patients do not respond to induction therapy (primary non-response) and a significant proportion loses response over time (secondary non-response). Very often patients profile in randomized controlled trials is quite restrictive and not representative of patients routinely treated under usual clinical conditions, especially, in terms of presence co-morbidities, concomitant treatments and previous use of biologics.

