## 6. Methodology

### 6.1. Study design

In order to meet the objectives of the present study, a retrospective, non-interventional, multicentre observational study including 25 gastroenterology sites from all around Spain has been designed. Participating investigators will be gastroenterologists and will include consecutive patients diagnosed with UC or CD that started treatment with biologics between June 2011 and June 2013, after giving written informed consent. The study will consist of one only visit in which investigators will collect patients' sociodemographic (age, gender, race, level of education, smoking habits alcohol intake) and clinical (concomitant diseases, date of diagnosis, previous treatment, current treatment, disease activity when starting treatment with biologics and at the study visit, current situation in terms of treatment with biologics) data from medical charts or directly from patients (in case of discrepancy, the information coming from medical charts will be preferable). Time since patients started biological treatment until study visit or until lack of treatment response or until treatment change will constitute the reference period for the study. In order to fulfill current legislations regarding non-interventional studies, investigators will commit to follow usual clinical practice.

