#### 6.4.4. Study variables

The following **sociodemographic variables** will be collected from patients' medical records or directly from patients during the study visit, straight after their inclusion in the study:

- Age
- Gender
- Race (caucasian, asiatic, latin, black, other)
- Level of education (uneducated, primary education, secondary education, university education)
- Working status (student, self-employed, employed by other, retired, housework, unemployed, temporarily unable to work, permanently unable to work, other)
- Smoking habits (non-smoker, ex-smoker, smoker, number of cigarettes per day)
- Alcohol intake (units per week).

The following **clinical variables** will be collected from patients' medical records (when available) or directly from patients during the study visit, straight after their inclusion in the study:

- Date of diagnosis (UD or CD).
- Disease activity at the beginning of the reference period and at the study visit through collection of the following variables:
  - For UC patients:
    - Partial Mayo Score (PMS) (9 point scale that excludes the endoscopic appearance of the mucosa)
    - General disease activity:
      - Mild: up to four bloody stools daily and no systemic toxicity
      - Moderate: four to six bloody stools daily and minimal toxicity
      - Severe: more than six bloody stools daily and signs of toxicity, such as fever, tachycardia, anaemia, raised erythrocyte sedimentation rate.
      - Fulminant: More than ten bloody stools daily, continuous bleeding, anaemia requiring blood transfusion, abdominal tenderness and colonic dilatation on plain abdominal radiographs.
    - Disease anatomic extent: proctitis, left-sided colitis or pancolitis.
    - Endoscopy findings:

- Normal or inactive disease
- Mild disease (erythema, decreased vascular pattern, mild friability)
- Moderate disease (marked erythema, lack of vascular pattern, friability erosions)
- Severe disease (spontaneous bleeding, ulceration).
- For CD patients:
  - Harvey-Bradshaw Index (HBI) (a simplified version of CDAI)
  - General disease activity:
    - Mild to moderate: ambulatory patients able to tolerate oral alimentation without manifestations of dehydration, toxicity, abdominal tenderness, painful mass, obstruction or >10% weight loss.

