    - Moderate to severe: failure to respond to treatment for mild disease, more prominent symptoms of fever, weight loss, abdominal pain or tenderness, intermittent nausea and vomiting without obstruction, or significant anemia.
    - Severe to fulminant: persisting symptoms on corticosteroids, high fevers, persistent vomiting, evidence of intestinal obstruction, rebound tenderness, cachexia, or evidence of abscess.
  - Disease behaviour: non-stricting and non-penetrating, stricturing and penetrating (fistulas and abscesses),
  - Disease location: terminal ileum.
- For CD and UC patients:
  - Stool frequency (normal number for this patient, 1-2 stools more than normal, 3-4 more stools than normal, 5 or more stools than normal)
  - Rectal bleeding (no blood seen, streaks of blood with stool less than half the time, obvious blood with stool most of the time, blood alone passes)
  - Urgency (hurry, immediately, incontinence)
  - Nocturnal stools (yes/no)
  - Need for antidiarrheal drugs (yes/no)
  - Constipation (yes/no)
  - Abdominal tenderness (none, mild and localized, mild to moderate and diffuse, severe or rebound)
  - Abdominal pain or cramping (none, mild, moderate, severe)
  - Anorexia (yes/no)
  - Nausea (yes/no)
  - Vomiting (yes/no)
  - Fever (yes/no)
  - Appetite loss
  - Weight loss (yes/no)
  - Fatigue (yes/no)
  - Night sweats (yes/no)

- Stunted growth (yes/no)
- Primary amenorrhoea (yes/no)
- General well-being (generally poor, fair, poor, terrible)
- Physician's global assessment (normal or quiescent disease severity, mild disease activity, moderate disease activity, severe disease activity)
- Other complications: severe profuse bleeding, massive bleeding due to ulceration, presence of stomach or duodenum ulceration, intestinal perforation, intraabdominal abscesses, stenosis, obstruction, fistulas, megacolon, others.
- Extraintestinal manifestations in UC and CD patients to be chosen from the following list according to ECCO guidelines:
  - Arthropathy and arthritis
  - Metabolic bone disease
  - Eye disease
  - Oral, aural and nasal disease
  - Skin disease
  - Hepato-pancreato-biliary disease
  - Neurological disease
  - Cardiovascular manifestations of IBD
  - Pulmonary manifestations of IBD

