- Urogenital manifestations of IBDComorbidities in UC and CD patients (defined as the coexistence of another medical condition alongside IBD, and does not imply causation) at the time of diagnosis and at the study visit, will be listed according to chosen according to the Charlson index:

Comorbidity Component	Score
Myocardial Infarction	1
Congestive Heart Failure	1
Peripheral Vascular Disease	1
Cerebrovascular Disease	1
Dementia	1
Chronic Obstructive Pulmonary Disease	1
Connective Tissue Disease	1
Peptic Ulcer Disease	1
Diabetes Mellitus	1 (mild), 2 (moderate- severe)
Moderate-Severe      Chronic      Kidney Disease	2
Hemiplegic	2
Leukemia	2
Malignant Lymphoma	2
Solid Tumor	2 (tumor), 6 (if metastasis)
Liver Disease	1 (mild), 3 (moderate-severe)
Acquired immunodeficiency syndrome (AIDS)	6

- Biological treatment/s for UC or CD followed during the reference period:
  - Starting date
  - Posology
  - Intensification of biological treatment: date and type of intensification
  - Continuing with the treatment
  - Date and reason for discontinuation, if applicable
  - New biological treatment prescribed after discontinuation, starting date, posology, continuing with the treatment, date and reason for discontinuation.
- Concomitant treatment with corticosteroids (e.g. prednisone, hydrocortisone, betamethasone, methylprednisolone, etc,) or immunosuppressives (e.g. Ciclosporin, Methotrexate, etc) during induction phase
  - Starting date, number of cycles

Other treatments followed before the reference period to be chosen from the following list:

- Aminosalicylates (e.g. mesalazine, Sulfasalazine, 5-ASA, etc), oral, enema, suppository.
- Corticosteroids (e.g. prednisone, hydrocortisone, betamethasone, methylprednisolone, etc), oral, enema, suppository.
- Thiopurines (e.g. azathioprine, mercaptopurine, etc).
- Immunosuppressives (e.g. Ciclosporin, Methotrexate, etc).
- Anti-diarrheal drugs.
- Pain medications.
- Antidepressants.
- Antibiotics.
- Use of alternative medicine (e.g. acupuncture, relaxation therapy, Qigong, herbal therapy, etc).
- Other (specify)

- Other treatments followed during the reference period to be chosen from the following list:
  - Aminosalicylates (e.g. mesalazine, Sulfasalazine, 5-ASA, etc), oral, enema, suppository.
  - Corticosteroids (e.g. prednisone, hydrocortisone, betamethasone, methylprednisolone, etc), oral, enema, suppository. Number of cycles
  - Thiopurines (e.g. azathioprine, mercaptopurine, etc).

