#### 6.4.5. Main outcome

Non responders will be those patients not achieving a reduction in HBI of at least 2 points from baseline for CD, and a decrease in the PMS of at least 2 points for UC.. In the cases where these indexes are not available, clinical response will be evaluated according to physician criteria at short term (10 weeks after starting the anti-TNF) and at long term (at least 6 months after starting the anti-TNF). Primary non-responders (PNR) were defined as patients with no clinical response at short term. Loss of response (LOR) was defined as loss of the effect of the drug along the follow up in a patient with initial response.

Reasons to stop the drug will be classified as follows: PNR, LOR, side effects (SE), remission and other.

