6.1. Biological treatment

We will describe the treatments administered to the patients:

- Number and percentage of patients who received each biological treatment (infliximab, adalimumab, golimumab and others).
- Number and percentage of patients who intensified the biological treatment and the reason (increased doses, decreased intervals between doses or both) according to the different biological treatment specified.
- Number and percentage of patients who discontinued the treatment and the reason (PNR, LOR, PR, SE, remission and others) according to the different biological treatment specified.
- Number and percentage of patients who received a second biological treatment and the description of the different biological treatments and the number of biological treatments received after discontinuation.
- Number and percentage of patients who received concomitant treatment with corticosteroids or immunosuppressives during induction phase. Description of the different concomitant treatment received.

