6.2. Treatments received before the reference period

- Number and percentage of patients who received at least one treatment before the reference period.
 - Number and percentage of patients who received aminosalicylates and the description of the treatments received (mesalazine, sulfasalazine, others).
 - Number and percentage of patients who received corticosteroids and the description of the treatments received (prednisone, hydrocortisone, methylprednisolone, Beclomethasone, budesonide, others).
 - Number and percentage of patients who received Immunosuppressives and the description of the treatments received (cyclosporin, methotrexate, azathioprine, mercaptopurine, others).
 - Number and percentage of patients who received anti-diarrheal drugs.
 - Number and percentage of patients who received pain medications.
 - Number and percentage of patients who received antidepressants.
 - Number and percentage of patients who received antibiotics.

- Number and percentage of patients who used alternative medicine and the description of the therapy received (acupuncture, relaxation therapy, Qigong, herbal therapy, others).
- Number and percentage of patients who received cannabis.
- Number and percentage of patients who received other treatments and the description of the treatment received.

6.3. Treatments received during the reference period (maintenance phase).

- Number and percentage of patients who received at least one concomitant treatment during the reference period (maintenance phase).
 - Number and percentage of patients who received aminosalicylates and the description of the treatments received (mesalazine, sulfasalazine, others).
 - Number and percentage of patients who received corticosteroids and the description of the treatments received (prednisone, hydrocortisone, methylprednisolone, Beclomethasone, budesonide, others).
 - Number and percentage of patients who received Immunosuppressives and the description of the treatments received (ciclosporin, methotrexate, azathioprine, mercaptopurin, others).
 - Number and percentage of patients who received anti-diarrheal drugs.
 - Number and percentage of patients who received pain medications.
 - Number and percentage of patients who received antidepressants.
 - Number and percentage of patients who received antibiotics.
 - Number and percentage of patients who used alternative medicine and the description of the therapy received (acupuncture, relaxation therapy, Qigong, herbal therapy, others).

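### SAP 7.1 can code a rescued loss of response as response maintained, and IBD surgery, unlike the other rescues, is not a prespecified variable

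*Protocol*

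**What the plan says.** **Surgery.** Protocol section 4 counts it among the main current treatments: "including thiopurines, methotrexate, tacrolimus, cyclosporine, and biological therapies), and surgery". In Protocol 6.4.4 the list introduced by "Other treatments followed during the reference period to be chosen from the following list" holds drug classes, alternative medicine and an open entry for anything else; the list for the time before the biologic is similar. Complications are prompted ("intestinal perforation, intraabdominal abscesses, stenosis, obstruction, fistulas, megacolon, others"), but an operation for them is not. Intensification, discontinuation, the next biologic and the number of steroid cycles are all recorded.

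The SAP does not fill the gap. SAP 6.1 plans "Number and percentage of patients who discontinued the treatment and the reason (PNR, LOR, PR, SE, remission and others"), which exists only for patients who stop the drug and has no surgery category. SAP 6.2 and 6.3 add an item that Protocol 6.4.4 lacks ("Number and percentage of patients who received cannabis") but no surgery item. The candidate variables in SAP 7.2 and the table index in Appendix 1 have none either.

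**Loss of response.** Protocol 6.4.5 defines it as "loss of the effect of the drug along the follow up in a patient with initial response". Protocol 6.1 says that the time from biologic start "until study visit or until lack of treatment response or until treatment change will constitute the reference period for the study". Scores are to be collected as follows: "Disease activity at the beginning of the reference period and at the study visit through collection of the following variables"; no other time after baseline is given.

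SAP 7.1 works differently. From 6 months on, a patient without a 2-point fall in the index is a loss. The physician's judgement is used only if the index is missing. The definition does not state that the patient must first have responded, does not look at what happened in between, and does not apply the end of the reference period.

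**The concern.** Loss of response is one of the two dependent variables for the primary objective (Protocol 7.4, SAP 7.2). A rule that looks at one late score cannot tell a patient who never lost response from one who lost it and was then brought back by something else.

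There is time for this to happen. Biologics were started between June 2011 and June 2013, and the protocol cites a consensus paper from 2016. Even the last starters would therefore be seen about 2.5 years or more after starting.

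For recorded rescues, an analyst could later check how many maintained patients were intensified, given steroids or switched, although the SAP plans no such check. For surgery in a patient who stays on the biologic, no dedicated field exists, so the check would mean going back to the charts.

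Coding some true losses as maintained pulls a real association towards 1 if it happens equally often with and without co-morbidity. If the frequencies differ, the odds ratio can move either way, even when there is no true association.

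**Working it through.** **1. The plan's own figure.** Protocol 7.1: 10 events per variable × 10 variables ÷ 0.50 = 200 per disease, 400 in total. This reproduces and is not in dispute; it supplies the base for step 3.

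**2. Tracing one patient through SAP 7.1.**
- The patient responds at 10 weeks, later loses response, is operated on for active disease and stays on the biologic.
- At the study visit the HBI is at least 2 points below baseline.
- The index is available, so the physician's judgement is not called on. SAP 7.1 codes response maintained.
- Under Protocol 6.4.5 the same patient is a loss, and under Protocol 6.1 the visit score falls after the reference period.

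Using the visit score as the long-term index is an inference: SAP 7.1 gives only a lower limit of 6 months, and Protocol 6.4.4 names no other time after baseline. The path is clearest in CD, because after colectomy in UC an index may be missing and the physician then decides.

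**3. Size, for surgery only.** From the documents: 400 patients and 50% response, read here as initial response. Assumed, because the documents give no figures: 40% of initial responders lose response; a share s of these are operated on, stay on the biologic and score at least 2 points below baseline.

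- Initial responders: 400 × 0.50 = 200. Losses: 200 × 0.40 = 80.
- Miscoded: 80 × 0.02, 0.05, 0.10 = 1.6, 4, 8. In CD alone (40 losses): 0.8, 2, 4.
- If Protocol section 4's figure of up to 30% primary non-response is used instead: 400 × 0.70 = 280 responders, 280 × 0.40 = 112 losses, and 2.2, 5.6 or 11.2 miscoded.

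Observed loss is q = p × (1 − s), and the observed OR is [q1/(1 − q1)] ÷ [q0/(1 − q0)], where 1 means with and 0 without co-morbidity. With p0 = 0.40, a true OR of 2.0 gives p1 = 0.5714.

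| True OR | s without / with co-morbidity | q0 | q1 | Observed OR | With s reversed |
|---|---|---|---|---|---|
| 2.0 | 2% / 2% | 0.392 | 0.560 | 1.97 | – |
| 2.0 | 5% / 5% | 0.380 | 0.543 | 1.94 | – |
| 2.0 | 10% / 10% | 0.360 | 0.514 | 1.88 | – |
| 1.0 | 5% / 2% | 0.380 | 0.392 | 1.05 | 0.95 |
| 1.0 | 10% / 5% | 0.360 | 0.380 | 1.09 | 0.92 |
| 1.0 | 25% / 10% (extreme) | 0.300 | 0.360 | 1.31 | 0.76 |

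With a true OR of 1, equal s leaves it at 1.00.

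**4. Sampling error for comparison.** Assume that 20% of the 200 responders have a co-morbidity: 16 losses and 24 maintained with it, 64 and 96 without. SE = √(1/16 + 1/24 + 1/64 + 1/96) = 0.361, and exp(±1.96 × 0.361) gives 0.49 to 2.03.

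**5. Why the reason for surgery is needed.** Suppose every operation were counted as a loss, and 5% of true maintainers without and 2% with co-morbidity were operated on for other reasons. Then q0 = 0.40 + 0.60 × 0.05 = 0.430, q1 = 0.40 + 0.60 × 0.02 = 0.412, and a true OR of 1 becomes 0.93.

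**The case against.** The strongest reply is that the protocol already has the right outcome. With the definition in 6.4.5 and the cut-off in 6.1, a patient who loses response is a loss before any operation, and the later score does not count. Protocol 7.3 presents the SAP as adding detail, not as replacing definitions. On this view the fault is an inconsistency between SAP and protocol, and it affects every rescue alike. This stands, and it is why the outcome rule comes first in the fix. A surgery field alone would leave patients rescued by intensification, steroids or a switch miscoded.

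It also stands that the chain of events is long, that retrospective charts will often lack an index so that the physician decides, and that the numbers above are small.

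Two parts of the reply do not remove the point. First, SAP 7.1 is the operational rule for the analysis, and as written it uses neither protocol provision. Secondly, surgery might be entered under other treatments, other complications or another stop reason. But those entries are unprompted, the SAP does not link them to the outcome, and the last does not exist for a patient who continues. The eCRF is not among the documents, and the cannabis item shows that Protocol 6.4.4 is not exhaustive, so a surgery field there cannot be ruled out. Even so, nothing in the SAP would use it.

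**Conclusion.** The point holds as a cheap improvement, likely small in effect. SAP 7.1 departs from the protocol's definition of loss of response, so a rescued loss can be coded as maintained. Surgery is the one rescue discussed here without a prespecified variable.

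Under assumed surgery-related rates of 2% to 10% of losses, about 2 to 8 patients are affected. A true OR of 2.0 becomes 1.97 to 1.88, and a true OR of 1 moves at most to between 0.92 and 1.09, against a null interval of 0.49 to 2.03. The loss rate, the surgery shares and the co-morbidity prevalence are all assumptions. No estimate is offered for the other rescues; their records allow a count.

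A reader might infer more: that the primary odds ratios are materially biased, or that operated patients cannot be found at all. The documents support neither. They give no surgery rate, the direction is unknown, only the extreme 25% against 10% case produces a sizeable shift, and open entries or the charts could still reveal operations. What can be said is that, without the field and the rule, the sponsor could not readily show that the effect is negligible.

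**What to change.** 1. **Outcome rule, SAP 7.1.** Code loss of response by the Protocol 6.4.5 definition, among initial responders. Do not let an index recorded after a documented loss of response, or after surgery for active IBD, count as maintained response. Classify those patients by the physician's criteria on their status up to that event. State that this includes events before 6 months, which otherwise have no qualifying assessment.
2. **Surgery item, Protocol 6.4.4 and the eCRF.** Collect IBD surgery (yes/no, date, reason) from biologic start to the study visit. Stopping at the end of the Protocol 6.1 reference period would miss operations that follow a loss. Define surgery for active disease by the recorded reason, and tabulate surgery by disease in SAP section 6.
3. **One sensitivity model.** Count surgery for active disease during biologic treatment, in initial responders, as loss of response, keeping these patients in the model.

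The cost is a few extra chart fields, a retrospective physician classification for the affected patients, one table and one model run. The main drawback is that a judgement replaces a score in those patients.
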